6.12.2 Assessing Severity of Adverse Events

The assessment of severity must be based on the Investigator's clinical judgement. Maximum severity should be assigned to one of the following categories:

- **Mild:** An AE which is easily tolerated by the subject, causing minimal discomfort and not interfering with everyday activities.
- **Moderate:** An AE which is sufficiently discomforting to interfere with normal everyday activities.
- **Severe:** An AE which prevents normal everyday activities.

An AE which is assessed as severe should not be confused with a serious AE. Refer to Section 6.12.5 for the definition of a serious AE.

6.12.3 Assessing Relationship to Study Treatment

Items to be considered when assessing the relationship of an AE to the study treatment are as follows:

- Temporal relationship of the onset of the event to the initiation of the study treatment
- The course of the event, considering especially the effect of discontinuation of study treatment or reintroduction of study treatment, as applicable
- Whether the event is known to be associated with the study treatment or with other similar treatments
- The presence of risk factors in the study subject known to increase the occurrence of the event
- The presence of non-study treatment related factors which are known to be associated with the occurrence of the event

Only AEs thought to be caused by IMP should be recorded as "related to IMP".

6.12.4 Classification of Causality

The relationship of an adverse event to the administration of the study drug is to be assessed according to the following definitions:

- No (unrelated, not related, no relation) – The time course between the administration of study drug and the occurrence or worsening of the adverse event rules out a causal relationship and another cause (concomitant drugs, therapies, complications, etc.) is suspected.
- Yes (related) – The time course between the administration of study drug and the occurrence or worsening of the adverse event is consistent with a causal relationship and no other cause (concomitant drugs, therapies, complications, etc.) can be identified. The definition implies a reasonable possibility of a causal relationship between the event and the study drug. This means that there are facts (evidence) or arguments to suggest a causal relationship.

Not Related: A causal relationship between the study treatment and the AE is not a reasonable possibility.

Related: A causal relationship between the study treatment and the AE is a reasonable possibility. The Investigator must further qualify the degree of certainty as “**possible**,” “**probable**”, or “**definite**.”

6.12.5 Serious Adverse Events

6.12.5.1 Definition of Serious Adverse Events

A serious adverse event (experience; SAE) or reaction is any untoward medical occurrence which:

- Results in death
- Is life-threatening (Note: The term “life-threatening” in the definition of “serious” refers to an event in which the subject was at risk of death at the time of the event; it does not refer to an event which hypothetically might have caused death if it were more severe.)
- Requires inpatient hospitalization or prolongation of existing hospitalization

NOTE: Any hospital admission with at least one overnight stay will be considered an inpatient hospitalization. An emergency room visit without hospital admission will not be recorded as a serious adverse event (SAE) under this criterion, nor will hospitalization for a procedure scheduled or planned before signing of informed consent. However, unexpected complications and/or prolongation of hospitalization that occur during elective surgery should be recorded as AEs and assessed for seriousness.

- Results in persistent or significant disability/incapacity
- Is a congenital anomaly/birth defect.
- Is determined to be an important medical event (at the discretion of the Investigator)

Medical and scientific judgment should be exercised in deciding whether expedited reporting is appropriate in other situations, such as important medical events that may not be immediately life-threatening or result in death or hospitalization but may jeopardize the subject or may require intervention to prevent one of the other outcomes listed in the definition above. These should also usually be considered serious.

The following hospitalizations are not considered to be SAEs because there is no “AE” (i.e., no untoward medical occurrence) associated with the hospitalization:

- Planned hospitalizations required by the protocol
- Hospitalization planned prior to informed consent (where the condition requiring the hospitalization has not changed post study drug administration)

6.12.5.2 Reporting Serious Adverse Events (SAEs)

Initial Reports

All SAEs occurring from the time of informed consent through the early termination/final visit and for 30 days following study drug discontinuation, whichever is longer, must be reported to Medpace Clinical Safety **within 24 hours** of the knowledge of the occurrence (this refers to any adverse event that meets any of the aforementioned serious criteria). All serious adverse events that the investigator considers related to study drug occurring after the 30-day follow-up period must be reported to the Sponsor.

To report the SAE, complete the SAE form electronically in the electronic data capture (EDC) system for the study. When the form is completed, Medpace Safety personnel will be notified electronically and will retrieve the form. If the event meets serious criteria and it is not possible to access the EDC system, send an email to Medpace Safety at [contact] or call the Medpace SAE hotline (phone number listed below), and fax the completed paper SAE form to Medpace (fax number listed below) within 24 hours of awareness. When the EDC system becomes available, the SAE information must be entered within 24 hours of the system becoming available.

Safety Contact Information:

Medpace Clinical Safety
Medpace SAE hotline – USA:
[contact], ext. 2999 **or** [contact], ext. 2999
[contact] **or** [contact]
e-mail: [contact]

Follow-Up Reports

The investigator must continue to follow the subject until the SAE has subsided or until the condition becomes chronic in nature, stabilizes (in the case of persistent impairment) or the subject dies.

Within 24 hours of receipt of follow-up information, the investigator must update the SAE form electronically in the EDC system for the study and submit any supporting documentation (e.g., subject discharge summary or autopsy reports) to Medpace Clinical Safety via fax or e-mail. If it is not possible to access the EDC system, refer to the procedures outlined above for initial reporting of SAEs.

The Investigator should notify the IRB/ IEC of the occurrence of the SAE, in writing, in accordance with local requirements. A copy of this communication must be forwarded to the clinical research associate (CRA) and filed in the trial master file (TMF).

6.12.5.3 Pregnancy Reporting

Any pregnancy where the estimated date of conception occurred either prior to the study termination visit or within 30 days of last study treatment must be reported. The pregnancy must be reported to Medpace Clinical Safety within 24 hours (from the time the pregnancy is detected). Medpace Clinical Safety will then forward the Exposure In Utero form to the PI or SI for completion.

If an adverse outcome of a pregnancy is suspected to be related to study drug exposure, this should be reported, regardless of the length of time that has passed since the exposure to study treatment.

A subject becoming pregnant while on study drug will immediately be withdrawn from the study and early termination study procedures will be performed.

The subject should be followed by the PI or SI until completion of the pregnancy. If the pregnancy ends for any reason before the anticipated date, the PI or SI should notify Medpace Clinical Safety. At the completion of the pregnancy, the PI or SI will document the outcome of the pregnancy. If the outcome of the pregnancy meets the criteria for immediate classification as an SAE (i.e., postpartum complication, spontaneous abortion, stillbirth, neonatal death, or congenital anomaly), the PU or SI should follow the procedures for reporting an SAE.

6.12.6 Regulatory Reporting of Adverse Events

AEs will be reported to the regulatory authorities in compliance with local and regional law and established guidance by the Sponsor or by a third party acting on behalf of the Sponsor. The format of these reports will be dictated by the local and regional requirements.

6.13 Clinical Laboratory Tests

Blood samples for steroids and steroid intermediate testing, synthetic glucocorticoid levels, hematology, serum chemistry, coagulation and urinalysis will be obtained at Screening, at the start of the Baseline Lead-in Period, at the start of every dose level (Day 1), at the start of every placebo Washout Period (Day 15) and at the Final Study Visit or the Early Termination Visit (Day 29).

Study visits that require blood sample collection for steroid hormones, must adhere to the following:

- Morning dose of replacement GC and MC must not be given until after the blood sample is collected
- Blood sample collection must be done prior to **10:00AM**

If both of these conditions are not met, the blood sample for efficacy endpoints must not be collected and another study visit must be scheduled for the next day or as soon as feasible.

Approximately 7 mL of blood will be collected for serum chemistry, 3 mL of blood for hematology and 3 mL of blood for PT/aPTT/INR. Approximately 20 mL of blood will be collected for steroid hormone testing and approximately 10 mL of blood will be collected for synthetic glucocorticoid testing. (See Table 5). Testing will be carried out by a central laboratory per the laboratory manual.

Subjects do not need to fast before the blood tests and will be in a seated or supine position during blood collection. Sampling time will be recorded on the eCRF.

For female subjects who are not surgically sterile or who have not been naturally post-menopausal for at least 12 consecutive months (i.e., who has had menses any time in the

preceding 12 consecutive months), serum pregnancy tests (β -hCG) will be performed at Screening. A urine pregnancy test (UPT) will be obtained prior to the first dose at each dose level on Day 1. A UPT will also be obtained at the Final Study Visit or Early Termination Visit. Sampling time will be recorded on the eCRF.

Blood samples for serology (HBsAg, Hepatitis C antibody and HIV) will be obtained at Screening. Approximately 4 mL of blood will be collected for serology.

Abnormal, clinically significant results may be verified to rule out laboratory error. Persistent relevant abnormal values must be followed up until the cause is determined or until they return to the previous values. Abnormal laboratory findings that are considered clinically significant by the PI/SI should be recorded as AEs (see Section 6.12.1).

Table 5 List of Clinical Laboratory Tests.

Hematology	Hematocrit (Hct), Hemoglobin (Hgb), Platelet count, Red blood cell (RBC) count, White blood cell (WBC) count with differential, Hemoglobin A1c
Serum Chemistry	Albumin (ALB), Alkaline phosphatase (ALK-P), Alanine aminotransferase (ALT; SGPT), Aspartate aminotransferase (AST; SGOT), Blood urea nitrogen (BUN), Calcium (Ca), Creatinine, Glucose, Total bilirubin, Total protein, Serum electrolytes (magnesium, sodium, potassium, chloride, bicarbonate),
Coagulation	PT/aPTT, INR
Urinalysis	Appearance, Bilirubin, Color, Glucose, Ketones, Microscopic examination of sediment, Nitrite, Occult blood, pH, Protein, Specific gravity, Urobilinogen
Steroid Hormones and intermediates	Glucocorticoid pathway : 17-OHP, progesterone, cortisol Mineralocorticoid pathway : 11-DOC; PRA; aldosterone Androgens : androstenedione, total testosterone, free testosterone, SHBG, DHEA, DHEAS Adrenocorticotrophic hormone (ACTH)
Synthetic Glucocorticoid Screen	Betamethasone, Budesonide, Dexamethasone, Fludrocortisone, Flunisolide, Fluorometholone, Hydrocortisone, Megestrol acetate, Methylprednisolone, Prednisolone, Prednisone, Triamcinolone, Triamcinolone acetonide
Pregnancy Testing	Serum and Urine Pregnancy Tests (β -hCG)
Serology	Hepatitis B surface antigen (HBsAg), Hepatitis C antibody, Human immunodeficiency virus (HIV)

6.13.1 Sample Collection, Storage, and Shipping

Sample collection, storage and shipment procedures for clinical laboratory samples will be provided in the laboratory manual.

6.14 Blood Sample Collection

In total, approximately 687 mL of blood will be collected during the study from each subject enrolled that continues through all five dose levels. This consists of approximately 173 mL for safety, 124 mL for PK, 390 mL for pharmacodynamic sampling.

6.15 Removal of Subjects from the Study or Study Drug

In accordance with the Declaration of Helsinki and subsequent conferences, subjects have the right to withdraw from the study at any time for any reason. The PI/SI and the Sponsor also have the right to withdraw subjects from the study. Subjects may be removed from the study for the following reasons:

1. In the PI or SI's judgment, administration of study drug would be detrimental to the subject's health.
2. The subject withdraws consent for continued participation or refuses further treatment with the investigational product.
3. The subject is noncompliant with the protocol.
4. The subject becomes pregnant.
5. The subject dies.
6. The subjects experiences an SAE or medically important event that would preclude further treatment with study drug
7. Need to initiate therapy with an excluded medication

Subjects should return to the investigational site for a Final Study Visit or Early Termination Visit after withdrawal/removal from the clinical trial. The reason for and date of withdrawal/removal from the clinical trial will be documented in the subject's medical records. Investigational site personnel must attempt to determine whether the reason for withdrawal was an AE, and if so, this must be reported in accordance with the procedures provided in Section 6.12. For all subjects who do not complete the clinical trial, regardless of the duration of treatment, all relevant information related to the withdrawal/removal will be entered into the eCRF.

Subjects who withdraw or are removed from the clinical trial may be replaced at the discretion of the Sponsor. All enrolled subjects will be fully accounted for and documented in the final clinical study report (CSR).

7 STUDY ACTIVITIES

Visit time points are intended as targets, and variations may be made to allow for logistical considerations and to accommodate scheduling conflicts. Refer to Section 6.1.

7.1 Screening Visit (Day -21 to Day -1)

Prior to any screening evaluations, written informed consent must be obtained. All Screening procedures are to be completed within a 21 day window.

The following procedures are to be performed at the Screening Visit:

- Review and signature of the ICF
- Review of inclusion/exclusion criteria
- Recording of medical history, demographics data, prior and concomitant medication history
- Complete physical examination
- Vital signs (including blood pressure, pulse, respiration, height, body weight and temperature)
- 12-lead ECG
- Blood sampling for hematology, serum chemistry, PT/aPTT/INR
- Urinalysis
- Blood sampling for serology
- **Blood sampling for steroids/steroid intermediates (before 10 AM) only if the replacement steroids (GC/MC) have not been dosed that morning**
Note: The test may be repeated one time at the Investigator's discretion if there is reason to suspect the results are inaccurate.
- Blood sampling for exogenous glucocorticoid levels.
- Serum pregnancy testing (β -hCG) for females who are not surgically sterile or who have not been naturally postmenopausal for at least 12 consecutive months (i.e., who have had menses any time in the preceding 12 consecutive months)
- AE reporting, if applicable
- Scheduling of next visit (Baseline Lead-in Period)
- Provide instructions to hold GC and MC morning dose prior to the next visit.

7.2 Baseline Lead-in Period

The following procedures are to be performed on Day 1 of the Baseline Lead-In Period:

- Vital signs (including blood pressure, pulse, respiration, body weight and temperature)
- Brief physical examination
- Review concomitant medications
- Review inclusion/exclusion criteria to confirm eligibility
- Blood sampling for hematology, serum chemistry, PT/aPTT/INR (subjects do not need to fast)
- AE reporting, if applicable

- **Blood sampling for steroids/steroid intermediates (before 10 AM) only if the replacement steroids (GC/MC) have not been dosed that morning**
- Blood sampling for exogenous glucocorticoid levels.
- Dispense IMP (Important Reminder: Subject is to remain blinded as to whether treatment is ATR-101 or placebo)
- Provide instructions to hold GC and MC morning dose prior to the next visit.

7.3 Dose Level 1, Days 1-28

ATR-101 Treatment Period, Days 1-14

The following procedures are to be performed on Day 1 of the ATR-101 dosing period:

Prior to dosing on Day 1

- Re-confirm eligibility based on inclusion/exclusion criteria (Note: Screening and Baseline visit 17-OHP level must be > 4x ULN)
- Confirm that the morning dose of replacement steroids (GC/MC) was not taken
Note: If the morning dose of replacement GC and MC was taken the visit cannot be performed. The visit must be rescheduled for the next day or as soon as possible. Instruct the subject to continue taking their study drug with the last dose occurring the evening prior to the rescheduled visit.
- Confirm the day and time of the last dose of IMP
- Perform drug accountability and confirm compliance with IMP
- Review of concomitant medication
- Assess AEs
- Abbreviated physical examination
- Vital signs (including blood pressure, pulse, respiration, body weight and temperature)
- 12-lead ECG
- Urine pregnancy testing (β -hCG) for females who are not surgically sterile or who have not been naturally postmenopausal for at least 12 consecutive months (i.e., who have had menses any time in the preceding 12 consecutive months)
- Blood sampling for hematology, serum chemistry, PT/aPTT/INR (subjects do not need to be fasting)
- **Blood sampling for steroids/steroid intermediates (before 10 AM)**
- Blood sampling for exogenous glucocorticoid levels.
- Blood sampling for ATR-101 PK assessment (pre-dose)

Administer first dose ATR-101 125 mg (after consumption of food)

- Blood sampling for PK assessment at 1, 2, 3, and 4 hours post-dose
- 12-lead ECG 2 hours post-dose
- Dispense IMP for Days 1-14
- Recheck vital signs at 1, 2 and 4 hours post-dose
- Scheduling of next visit (Dose Level 1, Day 15)

- Provide instructions to hold GC and MC morning dose prior to the next visit.

Placebo Washout Period, Days 15-28

The following procedures are to be performed on Day 15 after the completion of the 14 day ATR-101 dosing period.

Prior to dosing on Day 15

- Confirm that the morning dose of replacement steroids (GC/MC) was not taken
Note: If the morning dose of replacement GC and MC was taken the visit cannot be performed. The visit must be rescheduled for the next day or as soon as possible. Instruct the subject to continue taking their study drug with the last dose occurring the evening prior to the rescheduled visit.
- Confirm the day and time of the last dose of IMP
- Perform drug accountability and confirm compliance with IMP from Days 1-14
- Review of concomitant medication
- Assess AEs
- Abbreviated physical examination
- Vital signs (including blood pressure, pulse, respiration, body weight and temperature)
- 12-lead ECG
- Blood sampling for hematology, serum chemistry, PT/aPTT/INR (subjects do not need to be fasting)
- **Blood sampling for steroids/steroid intermediates (before 10 AM)**
- Blood sampling for exogenous glucocorticoid levels.
- Blood sampling for ATR-101 PK assessment (trough levels)

Administer first dose of placebo (after consumption of food)

- Dispense IMP for Days 15-28
- Scheduling of next visit (Day 29)
- Provide instructions to hold GC and MC morning dose prior to the next visit.

7.4 Final Study Visit or Next Dose Level, Day 1

Subjects will return to the clinic immediately after the completion of the 14 day Placebo Washout Period (i.e. 29 days after starting the Dose Level). The PI or SI will review the 17-OHP results obtained on Day 15 and determine whether this visit will be conducted as the Final Study Visit or Dose Level 2, Day 1 Visit:

- If 17-OHP ≤ 2 x ULN, complete the Final Study Visit (see Section 7.6), or
- If 17-OHP > 2 x ULN, proceed to Dose Level 2, Day 1

The PI or SI must assess overall safety (i.e. brief physical exam, laboratory test results and AE reporting) prior to proceeding to Dose Level 2, Day 1.

7.5 Dose Levels 2, 3, 4 and 5

Dose Levels 2, 3, 4, and 5 will follow the same visit schedule and procedures as Dose Level 1 (Section 7.3 and 7.4). However, Dose Level 5 is the final dose level and the visit immediately following completion of the Level 5 Placebo Washout Period will be the Final Study Visit regardless of the Day 15 laboratory results.

7.6 Final Study Visit

The Final Study Visit will take place if the primary outcome measure is met (17-OHP ≤ 2 x ULN) or at the completion of Dose Level 5. The following procedures will be performed.

- Confirm that the morning dose of replacement steroids (GC/MC) was not taken or if taken confirm the day and time of the last dose
Note: If the morning dose of replacement steroids (GC/MC) was taken, it is acceptable to complete the Final Study Visit
- Confirm the day and time of the last dose of IMP
- Perform drug accountability and confirm compliance with IMP
- Review of concomitant medication
- Assess AEs
- Complete physical examination
- Vital signs (including blood pressure, pulse, respiration, body weight and temperature)
- 12-lead ECG
- Blood sampling for hematology, serum chemistry, PT/aPTT/INR
- Urinalysis
- Urine pregnancy testing (β -hCG) for females who are not surgically sterile or who have not been naturally postmenopausal for at least 12 consecutive months (i.e., who have had menses any time in the preceding 12 consecutive months)
- **Blood sampling for steroids/steroid intermediates (before 10 AM)**
- Blood sampling for exogenous glucocorticoid levels
- Blood sampling for ATR-101 PK assessment (trough levels)

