5.3.9 Glucocorticoid and Mineralocorticoid Replacement for CAH

Subjects must continue to receive GC and MC according to individual regimens established prior to entering the study. The regimen should remain as stable and unchanged as possible to minimize potential confounding effects on efficacy outcome measures. However, changes are permitted to ensure subject safety. It is not expected that ATR-101 will have a direct effect on GC replacement therapy as the GC synthetic pathway is already compromised in CAH. Therefore, decreasing cortisol precursors (i.e. 17-OHP) should have no effect on glucocorticoid requirements over the 14 day ATR-101 treatment period.

The timing of glucocorticoid replacement therapy may have an impact on the measurement of 17-OHP. Replacement steroids (GC and MC) must not be taken on the mornings when adrenal steroids/steroid intermediates are being assessed (i.e. Day 15) as this could confound efficacy endpoint measures. GC and MC replacement doses may be given after blood samples are obtained for laboratory assessments.

Approximately 75% of CAH subjects have deficiency in the mineralocorticoid pathway in addition to the GC pathway.⁵ Thus, the majority of subjects in this study are anticipated to be on MC replacement. ATR-101 inhibition of the MC pathway for these subjects should not have an effect on MC replacement therapy. Subjects that enter the study with sufficiently intact endogenous MC production may be impacted by suppression of this pathway by ATR-101. However, pharmacological doses of GC, especially shorter acting ones such as hydrocortisone, also confer MC activity and the need for replacement MC is not usually required.¹⁴

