6.11 Timing of Pharmacodynamic Blood Samples and Dosing of Replacement Steroids

Adrenal steroids and steroid intermediates have a diurnal rhythmicity with peak 17-OHP occurring at around 8:00 AM. Thus, it is extremely critical that the timing of sample collection for efficacy endpoints and dosing of replacement steroids be precise and consistent. Every attempt should be made to collect the sample between 8:00-9:00 AM, but no later than 10:00AM. Study visits that require blood sample collection for steroid hormones, must adhere to the following:

- Morning dose of replacement GC and MC must not be given until after the blood sample is collected
- Blood sample collection must be done prior to **10:00 AM**

If both of these conditions are not met, the blood sample for steroid hormones must not be collected; the visit procedures should not be performed and the study visit must be rescheduled for the next day or as soon as feasible. The subject should continue taking study drug with the last dose occurring the evening prior to the rescheduled visit.

Dosing of GC and MC may take place after collection of blood samples for adrenal steroids and steroid intermediates.

Approximately 20 mL of blood will be collected for steroid hormone testing and approximately 10 mL of blood will be collected for testing synthetic glucocorticoid levels. If exogenous GC levels are suspected of confounding the efficacy outcome measures, additional testing may be performed. Further details on sample collection and handling are provided in the Laboratory Manual.

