## 6.8 Primary Efficacy Analyses

The percentage of responders will be tabulated for the Safety Population overall. A responder is defined as a subject who meets the primary outcome measure of Day 15 17-OHP  $\leq 2 \times \text{ULN}$  (ULN adjusted as needed for the menstrual cycle phase of subjects who are premenopausal women) at any dose level.

The percentage of subjects showing “drug effect” will be tabulated for the Safety Population overall. A subject showing “drug effect” is defined as a subject who is a responder or who has a negative mean percentage change in 17-OHP from Day 1 to Day 15 for Dose Levels 1-5.

The percentage of responders and percentage of subjects showing “drug effect” will also be tabulated for the Per Protocol Population overall as a sensitivity analysis to test the robustness of the primary result.

The change and percentage change in 17-OHP will also be calculated from Day 15 to Day 1 of the next dose level as follows:

- Change and percentage change from Dose Level 1 Day 15 to *Dose Level 2 Day 1*
- Change and percentage change from Dose Level 2 Day 15 to *Dose Level 3 Day 1*
- Change and percentage change from Dose Level 3 Day 15 to *Dose Level 4 Day 1*
- Change and percentage change from Dose Level 4 Day 15 to *Dose Level 5 Day 1*
- Change and percentage change from Dose Level 5 Day 15 to *Final Study Visit (Visit Day 29)*

The percentage of placebo responders will be tabulated for the Safety Population overall. A placebo responder is defined as a subject who meets Day 1/Final Study Visit 17-OHP  $\leq 2 \times \text{ULN}$  at any dose level, i.e. the 17-OHP at the italicized visit above is  $\leq 2 \times \text{ULN}$ .

The percentage of subjects showing “placebo effect” will be tabulated for the Safety Population overall. A subject showing “placebo effect” is defined as a subject who is a placebo responder or who has a negative mean percentage change in 17-OHP from Day 15 to Day 1 of the next dose level.

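### Protocol 7.6 and 7.7 conflict with 6.11 and 6.13 on steroid sampling after the morning replacement dose, and SAP 6.8 has no rule for the resulting Final Study Visit 17-OHP value

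*Protocol*

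**What the plan says.** **The general rule.** Protocol 6.11 covers every visit with steroid sampling and sets two conditions. One is the 10 AM limit. The other is "Morning dose of replacement GC and MC must not be given until after the blood sample is collected". If the conditions fail, "the blood sample for steroid hormones must not be collected; the visit procedures should not be performed and the study visit must be rescheduled". Protocol 6.13 names the Final Study Visit and the Early Termination Visit among its sampling visits, repeats both conditions and gives the same consequence: "the blood sample for efficacy endpoints must not be collected and another study visit must be scheduled for the next day". Protocol 7.3 applies the rule at Day 1 and Day 15, where a visit cannot go ahead if the dose was taken. Protocol 7.5 carries those procedures to Dose Levels 2 to 5.

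**The end-of-study visits.** Protocol 7.6 says "If the morning dose of replacement steroids (GC/MC) was taken, it is acceptable to complete the Final Study Visit", and its procedure list includes "Blood sampling for steroids/steroid intermediates (before 10 AM"), with no condition on the replacement dose. Protocol 7.7 repeats both items for early termination.

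**The analysis.** SAP 6.8 lists five washout changes in 17-OHP. Four end at Day 1 of the next dose level. The fifth runs from Dose Level 5 Day 15 to the Final Study Visit. It then states: "A placebo responder is defined as a subject who meets Day 1/Final Study Visit 17-OHP" at or below 2xULN, at any of the listed end visits. A placebo responder also counts as showing 'placebo effect'. No rule covers a value drawn after a replacement dose.

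**The concern.** A site whose subject has already taken the morning dose cannot follow both 6.11 and 7.6. If it follows 7.6 and draws every sample on the list, a 17-OHP value obtained under different conditions from all the others enters the washout data.

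This matters because the study has no parallel control arm. Protocol 3.2 relies on the washout to verify that steroid changes are due to ATR-101. Protocol 5.3.9 says GC timing may affect measured 17-OHP, and 3.3 says raised GC levels could lower ACTH and then 17-OHP. An affected final value would therefore tend to look like a response on placebo and to hide the return of 17-OHP after drug is stopped. The exposure is one-sided: 7.3 protects the Day 15 drug values and the Day 1 washout values, and only the end-of-study value is left open.

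**Working it through.** The plan states no figure on this point, so the check compares the texts and then sizes one affected value.

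**1. The rule if the morning GC/MC dose was taken**

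| Visit | Section | Visit goes ahead? | Steroid sample |
|---|---|---|---|
| Any steroid-sampling visit | Protocol 6.11 | No, reschedule | Not to be collected |
| Same, Final and Early Termination Visits named | Protocol 6.13 | Another visit to be scheduled | Not to be collected |
| Day 1 and Day 15, all dose levels | Protocol 7.3, 7.5 | No, reschedule | Not collected, as no visit |
| Final Study Visit | Protocol 7.6 | Acceptable to complete | Listed, 10 AM limit only |
| Early Termination Visit | Protocol 7.7 | Acceptable to complete | Listed, 10 AM limit only |

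The last two rows contradict the first two. Protocol 6.11 and 6.13 contain no exception for them.

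**2. Where SAP 6.8 uses the value**

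- Washout change: one of five listed, from Dose Level 5 Day 15 to the Final Study Visit.
- Placebo responder: any one listed end visit at or below 2xULN is enough. The definition points back to the five listed visits, so the only Final Study Visit it clearly covers is the one after Dose Level 5.
- 'Placebo effect': clearly entered through placebo-responder status only. The mean-change part is worded as Day 15 to Day 1 of the next dose level and does not name the Final Study Visit. SAP 6.9 is worded in the same way.

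**3. Effect of one reclassified subject**

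Shift in the placebo-responder percentage = 100 × 1/n, with n from 9 to 17 (Protocol 3.1, SAP 5.1):

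- n = 17: 100/17 = 5.9 points
- n = 9: 100/9 = 11.1 points

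This assumes that the subject was not already a placebo responder at an earlier Day 1 visit.

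**4. Illustration with assumed rates**

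The documents give no chance of a value at or below 2xULN on placebo. Assume five independent visits, chance q at each of the four Day 1 visits and q5 at the Final Study Visit. For a subject who completes all five levels, the chance of being a placebo responder is 1 − (1 − q)^4 × (1 − q5).

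| q | q5 = q | q5 = 10% | q5 = 20% | q5 = 30% |
|---|---|---|---|---|
| 2% | 9.6% | 17.0% | 26.2% | 35.4% |
| 5% | 22.6% | 26.7% | 34.8% | 43.0% |

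Example: 1 − 0.98^4 × 0.80 = 1 − 0.9224 × 0.80 = 26.2%. These rates show only how the any-visit definition responds to one less-protected visit. They are not estimates for this trial.

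**5. If the Final Study Visit were averaged into the 'placebo effect' mean**

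The wording does not clearly provide for this. A percentage change cannot fall below −100%, so one value could turn a five-change mean negative only if the other four sum to less than +100%, that is, average below +25%.

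**The case against.** The strongest reply is that 7.6 permits completing the visit, not drawing the steroid sample after the dose. The visit also covers a complete physical examination, ECG, safety laboratory tests, pregnancy test and drug accountability. On that reading 7.6 relaxes only the ban on visit procedures, the ban on the sample stays, and no affected 17-OHP value arises. This reading is available, so the harm is conditional. It does not remove the conflict: 6.11 also requires rescheduling, and 7.6 lists the sample without saying to omit it.

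Protocol 5.3.9 could be read as limiting the rule to one day: "Replacement steroids (GC and MC) must not be taken on the mornings when adrenal steroids/steroid intermediates are being assessed (i.e. Day 15"). That may narrow 5.3.9, but not 6.11 or 6.13, which cover all steroid-sampling visits.

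There are safeguards. Subjects are told at Day 15 to hold the morning dose before the next visit (7.3). The Final Study Visit confirms the time of any replacement dose and samples exogenous GC levels (7.6). Protocol 6.11 allows additional testing if exogenous GC is suspected of confounding. These may make the event rare and detectable. None of them tells the analyst what to do with the value.

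Three points in the plan's favour stand in full. The placebo measures are descriptive. For a subject who completes Dose Level 5, the other four washout values are protected. Any bias of this kind would raise the apparent placebo response, and so count against ATR-101.

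**Conclusion.** The protocol contradiction is real, and SAP 6.8 lacks a rule for its consequence. A Final Study Visit 17-OHP drawn after the morning dose could inflate the placebo-responder percentage, by 5.9 to 11.1 points per reclassified subject, and blunt the Dose Level 5 washout rebound. This rests on the direction given in Protocol 3.3 and on the sample actually being drawn. The documents give neither frequency nor size.

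A reader might infer more than the documents support:

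- *That false placebo responders will occur.* This is possible but not shown. Subjects enter at 4xULN or above, most are expected to be markedly higher (Protocol 3.3), and the placebo-responder limit is 2xULN. From an entry value of exactly 4xULN, that needs a fall of half.
- *That every subject's Final Study Visit feeds the SAP comparison.* SAP 6.8 explicitly lists only the visit after Dose Level 5. For a subject who responds at Levels 1 to 4, the Final Study Visit is the only washout reading after the responding dose, but the list defines no change for it.
- *That the main result is at risk.* Day 15 response, dose advancement and the Stage 1 rules do not use the Final Study Visit value.
- *That the 10 AM limit is also relaxed.* Protocol 7.6 and 7.7 keep it.

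**What to change.** 1. Reconcile Protocol 7.6 and 7.7 with 6.11 and 6.13, so that a site has one instruction for the visit and one for the steroid sample when the morning dose has been taken. Which rule to adopt is for the sponsor and investigators to decide.
2. In SAP 6.8, flag and list any Final Study Visit 17-OHP drawn after the morning GC/MC dose. Present the washout change and the placebo-responder tabulation without those values, and show the same tables with all values as a sensitivity analysis.

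The inputs are already collected: the time of the last replacement dose is confirmed at the visit (Protocol 7.6), sampling time goes on the eCRF (6.13), and GC and MC have their own eCRF (5.3.8). The cost is a wording change and one data-handling rule. The downside is that a few washout values drop out of a descriptive table.
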